15.2.3. Severity of Events

The following definitions should be considered when evaluating the severity of AEs and SAEs:

Severity of Event	
Mild	Symptoms barely noticeable to subject or does not make subject uncomfortable; does not influence performance or functioning; prescription drug not ordinarily needed for relief of symptoms but may be given because of personality of subject.
Moderate	Symptoms of a sufficient severity to make subject uncomfortable; performance of daily activity is influenced; subject is able to continue in study; treatment for symptoms may be needed.
Severe	Symptoms cause severe discomfort; symptoms cause incapacitation or significant impact on subject’s daily life; severity may cause cessation of treatment with study treatment; treatment for symptoms may be given and/or subject hospitalized.

15.2.4. Expectedness of Events

Expectedness of all AEs will be determined by Biogen according to the Investigator’s Brochure.

15.3. Monitoring and Recording Events

15.3.1. Adverse Events

Any AE experienced by the subject between the time of first dose of study treatment and the subject’s final clinic visit (including FU Visit) is to be recorded on the CRF, regardless of the severity of the event or its relationship to study treatment. At each study visit, the Investigator will assess the subject for AEs and will record any new AEs or updates to previously reported AEs on the CRF.

CONFIDENTIAL

The information contained herein may not be used, disclosed, or published without the written consent of Biogen MA Inc.

AEs that are ongoing when the subject completes or discontinues the study will be followed by the Investigator until the event has resolved, stabilized, or returned to baseline status. AE outcome will be recorded on the CRF, as applicable.

15.3.2. Adverse Events of Special Interest

An AE of special interest is an AE of scientific and medical concern specific to this study, for which ongoing monitoring and reporting are required. ARIA-E and ARIA-H are considered AEs of special interest and will be entered on the Adverse Event of Special Interest CRF within 72 hours following the receipt of abnormal MRI findings from the central MRI reader.

AE reporting for ARIA-E and ARIA-H will be based on the following centrally read MRI sequences: fluid attenuated inversion recovery/T2 for ARIA-E and T2*/gradient echo for ARIA-H.

If the event qualifies as an SAE, an SAE form should be submitted per the guidelines in Section 15.3.4. Investigators should include a copy of the centrally read MRI report when submitting the SAE form to Biogen.

15.3.3. Serious Adverse Events

Any SAE experienced by the subject between the time of the signing of the ICF and the subject's final clinic visit (including FU Visit) is to be recorded on an SAE form, regardless of the severity of the event or its relationship to study treatment. SAEs must be reported to Biogen within 24 hours as described in Section 15.3.4. Follow-up information regarding an SAE also must be reported within 24 hours. This also applies to SAEs that occur after administration of the ligand. FU information regarding an SAE also must be reported with 24 hours

Subjects will be followed for all SAEs until the final clinic visit (including FU Visit). Thereafter, the event should be reported to Biogen only if the Investigator considers the SAE to be related to study treatment.

Any SAE that is ongoing when the subject completes or discontinues the study will be followed by the Investigator until the event has resolved, stabilized, or returned to baseline status.

15.3.4. Immediate Reporting of Serious Adverse Events

In order to adhere to all applicable laws and regulations for reporting an SAE, the study site must formally notify Biogen within 24 hours of the site staff becoming aware of the SAE. It is the Investigator's responsibility to ensure that the SAE reporting information and procedures are used and followed appropriately.

CONFIDENTIAL

The information contained herein may not be used, disclosed, or published without the written consent of Biogen MA Inc.

Reporting Information for SAEs

A report **must be submitted** to Biogen regardless of the following:

- Whether or not the subject has undergone study-related procedures
- Whether or not the subject has received study treatment
- The severity of the event
- The relationship of the event to study treatment

To report initial or follow-up information on an SAE, fax or email a completed SAE form; refer to the Study Reference Guide's Official Study Contact List for country-specific fax numbers or email addresses.

15.3.4.1. Deaths

Death is an outcome of an event. The event that resulted in death should be recorded on the appropriate CRF. All causes of death must be reported as SAEs within 24 hours of the site becoming aware of the event. The Investigator should make every effort to obtain and send death certificates and autopsy reports to Biogen. The term death should be reported as an SAE only if the cause of death is not known and cannot be determined.

15.3.5. Suspected Unexpected Serious Adverse Reactions

Suspected unexpected serious adverse reactions (SUSARs) are SAEs that are unexpected and judged by the Investigator or Biogen to be related to the study treatment administered.

Appropriate personnel at Biogen will unblind SUSARs for the purpose of regulatory reporting. Biogen will submit SUSARs (in blinded or unblinded fashion) to regulatory agencies according to local law. Biogen will submit SUSARs to Investigators in a blinded fashion.

15.4. Procedures for Handling Special Situations

15.4.1. Pregnancy

Subjects should not become pregnant or impregnate their partners during the study and for 24 weeks after their last dose of study treatment. If a female subject becomes pregnant, study treatment must be discontinued *immediately*.

The Investigator must report a pregnancy occurring in a female subject by faxing the appropriate form to Biogen within 24 hours of the site staff becoming aware of the pregnancy. Refer to the Study Reference Guide's Official Study Contact List for complete contact information. The Investigator or site staff must report the outcome of the pregnancy to Biogen. A pregnancy is not considered an AE and should not be recorded on the AE CRF.

CONFIDENTIAL

The information contained herein may not be used, disclosed, or published without the written consent of Biogen MA Inc.

Congenital abnormalities and birth defects in the offspring of male or female subjects should be reported as an SAE if conception occurred during the study treatment period.

15.4.2. Overdose

An overdose is any dose of study treatment administered to a subject or taken by a subject that exceeds the dose assigned to the subject according to the protocol. Overdoses are not considered AEs and should not be recorded as an AE on the CRF; however, all overdoses must be recorded on an Overdose form and faxed to Biogen within 24 hours of the site becoming aware of the overdose. An overdose must be reported to Biogen even if the overdose does not result in an AE. If an overdose results in an AE, the AE must be recorded. If an overdose results in an SAE, both the SAE and Overdose forms must be completed and faxed to Biogen. All study treatment-related dosing information must be recorded on the dosing CRF.

15.4.3. Medical Emergency

In a medical emergency requiring immediate attention, site staff will apply appropriate medical intervention, according to current standards of care. The Investigator (or designee) should contact the study's Medical Director. Refer to the Study Reference Guide's Official Study Contact List for complete contact information.

15.4.3.1. Unblinding for Medical Emergency

In this study, emergency decoding will be made available to the Investigator and designated personnel at Biogen through IRT.

In a medical emergency when knowledge of the subject's treatment assignment may possibly influence the subject's clinical care, the Investigator may access the subject's treatment assignment by IRT. However, prior to unblinding, the Investigator can contact the 24-hour emergency medical support number at [REDACTED].

The Investigator must document the reasons for unblinding in the subject's source documents. The Investigator is strongly advised not to divulge the subject's treatment assignment to any individual not directly involved in managing the medical emergency or to personnel involved with the analysis and conduct of the study. The Investigator can contact Biogen to discuss such situations.

15.5. Contraception Requirements

All women of childbearing potential and all men must ensure that highly effective contraception is used during the study and for 24 weeks after their last dose of study treatment. In addition, subjects should not donate sperm or eggs for the duration of the study and for at least 24 weeks after their last dose of study treatment.

For the purposes of this study, women who do not meet one of the following criteria are considered to be physiologically capable of becoming pregnant and are, therefore, defined as women of childbearing potential:

CONFIDENTIAL

The information contained herein may not be used, disclosed, or published without the written consent of Biogen MA Inc.

- Postmenopausal
 - 12 continuous months of natural (spontaneous) amenorrhea without an alternative medical cause and a serum follicle-stimulating hormone level >40 mIU/mL
 - 6 weeks after surgical bilateral oophorectomy with or without hysterectomy
- Posthysterectomy
- Female surgical sterilization (e.g., bilateral tubal ligation), where applicable according to local guidelines

For the purposes of the study, highly effective contraception is defined as use of at least 1 of the following:

For females:

- Combined (estrogen and progesterone) hormonal contraception associated with inhibition of ovulation (oral, injectable, or implantable) or progestogen-only hormonal contraception associated with inhibition of ovulation (oral, injectable, or implantable).
- Placement of an intrauterine device or intrauterine hormone-releasing system.
- *Where applicable according to local guidelines*, barrier methods of contraception with use of a spermicide: condom or occlusive cap (diaphragm or cervical/vault caps) with spermicidal foam/gel/film/cream suppository. The use of barrier contraceptives should always be supplemented with the use of a spermicide.
- Bilateral tubal occlusion.
- Sex with a male who has undergone surgical sterilization (with the appropriate postvasectomy documentation of the absence of sperm in the ejaculate).

For males:

- Vasectomy with negative semen analysis at Follow-up Visit.
- Where applicable according to local guidelines, condoms with spermicide.
- Sex with a woman who uses the highly effective methods described above for females if she is of childbearing potential.

True abstinence, when this is consistent with the preferred and usual lifestyle of the subject, can be considered an acceptable method of contraception based on the evaluation of the Investigator who should also take into consideration the duration of the clinical study. Periodic abstinence (e.g., calendar, ovulation, symptothermal, postovulation methods) and withdrawal are not considered acceptable methods of contraception.

CONFIDENTIAL

The information contained herein may not be used, disclosed, or published without the written consent of Biogen MA Inc.

Pregnancy reporting is described in Section [15.4.1](#).

15.6. Safety Responsibilities

15.6.1. The Investigator

The Investigator's responsibilities include fulfilling all roles and responsibilities listed in Section [7.2](#). Additionally, the Investigator's responsibilities include the following:

- Monitor and record all AEs, including SAEs, on the CRF regardless of the severity or relationship to study treatment.
- Determine the seriousness, relationship, and severity of each event.
- Determine the onset and resolution dates of each event.
- Monitor and record all pregnancies and follow up on the outcome of all pregnancies in female subjects.
- Complete an SAE form for each SAE and fax it to Biogen within 24 hours of the site staff becoming aware of the event.
- Pursue SAE follow-up information actively and persistently. Follow-up information must be reported to Biogen within 24 hours of the site staff becoming aware of new information.
- Ensure all AE and SAE reports are supported by documentation in the subjects' medical records.
- Pursue AE follow-up information, if possible, until the event has resolved or become stable. Record AE follow-up information, including resolution, on the CRF, as applicable.
- Report SAEs to local ethics committees, as required by local law.

15.6.2. Biogen

Biogen's responsibilities include the following:

- Before a site can enroll any subjects, the Clinical Monitor (Biogen designee) is responsible for reviewing with site staff the definitions of AE and SAE, as well as the instructions for monitoring, recording, and reporting AEs and SAEs.
- Biogen is to notify all appropriate regulatory authorities, central ethics committees, and Investigators of SAEs, as required by local law, within required time frames.

CONFIDENTIAL

The information contained herein may not be used, disclosed, or published without the written consent of Biogen MA Inc.

16. STATISTICAL METHODS AND DETERMINATION OF SAMPLE SIZE

The objectives of the study and the endpoints to be analyzed are listed in Section 6. In general, study data will be summarized using standard descriptive statistics, and no formal statistical hypothesis testing is planned. Additional details of the analysis of study data will be provided in a separate Statistical Analysis Plan.

16.1. Demography and Baseline Disease Characteristics

Demographics and baseline data will be summarized by treatment group with summary statistics (mean, standard deviation, median, and range) or with frequency distributions.

16.2. Primary and Secondary Endpoint Analysis

16.2.1. Analysis Population

The safety population, defined as all subjects who were randomized and received at least 1 dose of aducanumab will be used for the primary and secondary endpoint analyses.

16.2.2. Method of Analysis

16.2.2.1. Analysis of the Primary Endpoint

No formal hypothesis testing is planned for the primary endpoint. The incidence rate and 90% exact binomial confidence interval (CI) for each treatment group will be provided. The rate difference between 2 groups and its 90% exact CI will be provided. The list of events specified in the primary endpoint (as determined by the Adjudication Committee; see Section 19.2.1) will be provided by group.

16.2.2.2. Analysis of the Secondary Endpoints

The incidence of ARIA and their severity by imaging as well as clinical perspectives, will be summarized for each group and overall. These analyses will also be performed for the different types of ARIA (e.g., ARIA-E, ARIA-H). Kaplan-Meier plots will be produced to describe time to ARIA onset, time to symptomatic ARIA, and time to asymptomatic ARIA. Summary statistics will be presented to describe the time to resolution of ARIA.

The incidence of AEs, SAEs, and antiaducanumab antibodies, as well as clinical changes in vital signs and ECGs, will be summarized for each group and overall.

CONFIDENTIAL

The information contained herein may not be used, disclosed, or published without the written consent of Biogen MA Inc.

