4.3.2.1.3. Study 221AD103

Currently available data on ARIA are mostly based on the ongoing Study 221AD103 of aducanumab in subjects with prodromal AD or mild AD dementia. This study comprises a completed double-blind, 1-year placebo-controlled period, followed by an ongoing LTE in which all subjects receive aducanumab via monthly infusions, in a dose-blinded fashion. A total of 185 subjects have been dosed with aducanumab, in the placebo-controlled period and/or the LTE.

Based on data available as of 25 May 2017 in a prespecified interim analysis, ARIA-E (with or without ARIA-H) has been detected in 25% of all aducanumab-treated subjects (46/185). In the 12-month placebo-controlled period, in subjects receiving aducanumab in a fixed-dose regimen,

CONFIDENTIAL

The information contained herein may not be used, disclosed, or published without the written consent of Biogen MA Inc.

the incidence of ARIA-E increased with dose and was higher in ApoE ε4 carriers than noncarriers (3% [1/31], 6% [2/32], 37% [11/30], and 41% [13/32] in the 1, 3, 6, and 10 mg/kg dose groups, respectively). However, the incidence of ARIA-E appeared to be lower in ApoE ε4 carrier subjects receiving titration to 10 mg/kg (35% [8/23]) than in carrier subjects receiving fixed doses (43% [9/21] and 55% [11/20]) of 6 and 10 mg/kg, respectively. Furthermore, among the 8 ApoE ε4 carrier subjects receiving titration to 10 mg/kg who had ARIA-E, the abnormalities were observed at the 3 and 6 mg/kg dose levels (5 and 3 subjects, respectively).

The incidence of isolated ARIA-H was similar in the placebo and aducanumab groups (7% [3/46] and 5% [7/148], respectively), which likely indicates a background finding in this population.

ARIA was typically observed early in the course of the treatment, with the majority of cases observed between the second and fifth doses. A total of 91% of subjects (42/46) developed the first episode of ARIA-E within the first 12 months of active dosing, with 76% of subjects (35/46) developing the first episode within the first 6 months of active dosing. In most cases, ARIA-E resolved 4 to 12 weeks after onset as assessed by MRI, and ARIA-H was typically stable within 2 to 4 weeks after onset.

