4.4. Study Rationale

During aducanumab's clinical development, the paradigm of its dosing during and after ARIA events has evolved over the years. In the ongoing aducanumab clinical studies (221AD103, 221AD301, and 221AD302), the protocol-defined dosing disposition mandates that subjects who are asymptomatic with mild severity on MRI continue dosing. Subjects with symptomatic ARIA, as well as those with asymptomatic ARIA that is moderate or severe on MRI, temporarily suspend or permanently discontinue dosing. Based on the current dosing regimen, data from Study 221AD103, although limited, have indicated that continuing dosing with aducanumab in subjects with asymptomatic mild ARIA was not associated with clinically significant negative outcomes (see Section 4.3.2.1.3).

Data on the impact of continuing dosing during ARIA events are available from other anti-A β mAb trials. In 3 Phase 2 studies of bapineuzumab, among 17% of subjects (36/210) who developed ARIA-E during treatment, the majority of cases (78% [28/36]) were asymptomatic [Sperling 2012]. A post hoc review revealed that 42% of asymptomatic subjects (15/36) were identified as having ARIA-E only during a retrospective MRI re-read central review. Of these, 13 subjects continued to receive bapineuzumab infusions while ARIA-E was present and remained asymptomatic.

In 2 Phase 3 studies of bapineuzumab in subjects with mild-to-moderate AD, the majority of ARIA-E cases were asymptomatic (85% of ApoE ϵ 4 carriers and 45% to 84% of ApoE ϵ 4 noncarriers, depending on the bapineuzumab dose) [Salloway 2014]. A retrospective MRI final read analysis identified treatment-emergent ARIA-E in 242 subjects, including 76 additional cases that were not detected previously [Ketter 2017]. The majority of missed ARIA-E cases (88%) had a radiological severity score ≤ 2 , and only 10% had a severity score ≥ 3 . Of the total ARIA-E cases, approximately 64% of ApoE ϵ 4 carriers and 52% of noncarriers were dosed through during an ARIA-E event. For all ARIA-E cases, radiological severity score for subjects who were dosed through events was comparable to those who discontinued treatment, except for a higher score for ApoE ϵ 4 noncarriers who were dosed through in the 0.5 mg/kg group. The only difference in the clinical presentation of subjects who were dosed through compared with those who discontinued treatment was the duration of the ARIA-E episodes, with a shorter duration in subjects who discontinued.

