Stage 2 (contingent on DSMC recommendation based on review of the Stage 1 data, Section 19.2.2)

- Any severity of MRI: *Continue dosing*

Note: To maintain the blind, placebo will be given to Group 1 subjects in prespecified cases of dose suspension/discontinuation due to asymptomatic ARIA in both Stages 1 and 2 (for details see Sections 11.2.1.1 and 11.2.1.2).

Management of symptomatic ARIA (any severity of MRI) and management of ARIA-H (macrohemorrhage) *will be the same in Groups 1 and 2* and will be generally consistent with that in the ongoing Phase 3 program, as follows:

Throughout the study, Group 1 and Group 2:

[figure not shown]
- Symptomatic ARIA, any severity on MRI:
 - *Suspend or permanently discontinue treatment*
- ARIA-H (macrohemorrhage) with or without symptoms
 - *Permanently discontinue treatment*

At the end of the 52-week randomized, controlled treatment period, subjects who meet entry criteria may enter an optional LTE period in which subjects will continue to receive infusions of aducanumab at 10 mg/kg every 4 weeks for an additional 104 weeks (a total of 40 doses). During this time, asymptomatic ARIA in all subjects will be managed according to the plan described for Group 2.

See [Figure 1](#) for a schematic of the study design.

CONFIDENTIAL

The information contained herein may not be used, disclosed, or published without the written consent of Biogen MA Inc.

Figure 1: Schematic of Study Design

* This study will evaluate the safety impact of continuing dosing in asymptomatic subjects with ARIA in a 2-stage approach. In Stage 1, Group 2 subjects with mild to moderate asymptomatic ARIA will be dosed through; it is planned that the impact of continuing dosing during asymptomatic ARIA that is mild, moderate, or severe on MRI (excluding ARIA-H [macrohemorrhage]) will be assessed in Stage 2, contingent upon DSMC recommendation after a review of Stage 1 data.

Note: All subjects are to receive titration to 10 mg/kg (2 doses of 1 mg/kg, then 2 doses of 3 mg/kg, then 2 doses of 6 mg/kg, then 10 mg/kg thereafter).

CONFIDENTIAL

The information contained herein may not be used, disclosed, or published without the written consent of Biogen MA Inc.

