11.2.1.1. ARIA-E Cases

The management and disposition of subjects who develop ARIA-E during the randomized treatment period are detailed in [Table 5](#).

All subjects who develop ARIA-E should have unscheduled visits every 4 weeks (± 5 days) for follow-up MRI and ARIA safety assessments (as detailed in Section 5, [Table 1](#)), until the ARIA-E has resolved per centrally read MRI. [REDACTED] PK samples will be collected at the first unscheduled visit following an episode of ARIA.

Subjects who continue dosing during the first or subsequent recurring ARIA-E events will do so in accordance with the aducanumab dosing regimen (for details, see Section 11.2.3).

Subjects for whom treatment is temporarily suspended due to the first or recurrent ARIA-E events may resume treatment at the same dose, once ARIA-E and (if present) clinical signs and symptoms have resolved, in the treating HCP's opinion (for details see Section 11.2.3).

Management of ARIA-E after it resolves is described in Section 11.2.4.

Subjects who continue dosing during an ARIA-E event or who suspend dosing (including due to an ARIA-E event) should complete all scheduled clinic visits for assessments (as detailed in Section 5, [Table 1](#)). Subjects who permanently discontinue treatment due to ARIA-E (as with subjects who discontinue for other reasons) are to remain in the study and follow a modified schedule for tests and assessments until the end of study or withdrawal of consent ([Table 4](#)). This is in addition to completing the unscheduled visits as described above.

Subjects who withdraw from the study are to return for a safety follow-up visit 18 weeks after their last dose of study treatment.

CONFIDENTIAL

The information contained herein may not be used, disclosed, or published without the written consent of Biogen MA Inc.

Table 5: Disposition of ARIA-E Cases During Randomized Treatment Period

Clinical Symptom Severity (if present)	ARIA-E Severity on MRI (Central Read)				
	Mild	Moderate	Severe		
Asymptomatic	Stage 1				
Group 1	Continue dosing at current dose and schedule	Suspend dosing and receive placebo . Once ARIA-E resolves the subject may resume dosing at the same dose.	Suspend dosing (without receiving placebo). Once ARIA-E resolves, subject may resume dosing at same dose		
Group 2	Continue dosing at current dose and schedule ¹				
Asymptomatic	Stage 2				

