11.2.1.2. ARIA-H (Microhemorrhage or Superficial Siderosis) Cases

The management and disposition of subjects who develop ARIA-H (microhemorrhage or superficial siderosis) is detailed in Table 6.

All subjects who develop ARIA-H (microhemorrhage or superficial siderosis) should have an unscheduled visit(s) every 4 weeks (± 5 days) for follow-up MRI and ARIA safety assessments, as detailed in Section 5 (Table 1), until the microhemorrhages/superficial siderosis are deemed stable (defined as no change or a decrease in the number, size, severity, or number of locations between 2 consecutive MRIs, which can include the initial MRI) per centrally read MRI.

██████████ PK samples will be collected at the first unscheduled visit following an episode of ARIA.

Subjects who continue dosing during the first or subsequent recurring ARIA-H events, will do so in accordance with the aducanumab dosing regimen (for details see Section 11.2.3).

Subjects for whom treatment is temporarily suspended due to a first or recurrent ARIA-H may resume treatment at the same dose once the ARIA-H is deemed stable and (if present) the clinical signs and symptoms have resolved in the treating HCP's opinion (for details see Section 11.2.3).

Management of ARIA-H after stabilization is described in Section 11.2.4.

Subjects who continue dosing through an ARIA-H event or who suspend dosing (including due to an ARIA-H event) should complete all scheduled clinic visits as detailed in Section 5 (Table 1). Subjects who permanently discontinue treatment due to an ARIA-H event (as with subjects who permanently discontinue treatment for other reasons) are to remain in the study and follow a modified schedule for tests and assessments until the end of study or withdrawal of consent (Table 4). The only exception is a subject who may develop severe asymptomatic ARIA-H in Stage 2 as outlined in Table 6; such a subject is to follow the regular visit schedule (Table 1) in order to maintain the blind to the subject's group assignment.

Subjects who withdraw from the study are to return for a safety follow-up visit 18 weeks after their last dose of study treatment.

CONFIDENTIAL

The information contained herein may not be used, disclosed, or published without the written consent of Biogen MA Inc.

Table 6: Disposition of ARIA-H (Microhemorrhage or Superficial Siderosis) Cases During the Randomized Treatment Period

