2 STATISTICAL ANALYSIS METHODS

2.1 General Considerations

Summary tables will be presented using descriptive summary statistics. For continuous variables, summary statistics will generally include: number of participants with data, mean, standard deviation, median, minimum and maximum. For categorical variables, this will generally include: number of participants in the analysis population, number with data, and the percent of those with data in each category. Due to the minimal amount of data collected in the study, most endpoints will not be summarized; instead, listings will be provided. Any straightforward listings that are routinely produced for Biogen clinical studies will not necessarily be mentioned in this plan.

Unless otherwise specified, summaries will be presented by study group and overall. Each table will typically have three columns, ordered as follows: Group 1, Group 2, and BIIB037 Total. Summaries presented by decreasing or increasing frequency will be sorted based on the aducanumab total column.

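### Does the missing rule for unresolved episodes in the time-to-ARIA-resolution summary call for a change to the plan?

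*Protocol*

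**What the plan says.** Time to resolution of ARIA on MRI, and of symptomatic ARIA, are secondary endpoints (Protocol section 6). Protocol 16.2.2.2 names Kaplan-Meier plots for three onset times; for resolution it says "Summary statistics will be presented to describe the time to resolution of ARIA". Section 16 describes the analysis as descriptive, without formal testing, and defers further detail to a separate SAP.

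Follow-up of an episode is set elsewhere in the protocol:

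- ARIA-E: unscheduled MRI visits every 4 weeks "until the ARIA-E has resolved per centrally read MRI" (11.2.1.1).
- ARIA-H: the same visits "until the microhemorrhages/superficial siderosis are deemed stable" (11.2.1.2), with stability defined there.
- Adverse events ongoing when a subject completes or discontinues are followed until resolved, stabilized or back to baseline (15.3.1). For a subject with events under follow-up, the end-of-study date is the date of resolution (7.1).
- Long-term extension: "During this time, asymptomatic ARIA in all subjects will be managed according to the plan described for Group 2" (section 7).

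The SAP was written after the study was terminated. Its Introduction calls most secondary endpoints not evaluable. Section 2.5.2.3 plans a summary of ARIA incidence plus listings, and the only ARIA table planned is Table 10, incidence.

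**The concern.** Time to resolution is a censored time, just as time to onset is, yet only onset gets a censored-data method. Elsewhere the documents use the phrase for ordinary descriptives: "summary statistics (mean, standard deviation, median, and range" in Protocol 16.1, and "summary statistics will generally include: number of participants with data, mean, standard deviation, median, minimum and maximum" in SAP 2.1. Read that way, an episode with no resolution date has no value and drops out.

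The endpoint bears on the randomized question. Protocol 4.4 reports that, with another antibody, the only clinical difference between subjects dosed through and those who stopped was "the duration of the ARIA-E episodes, with a shorter duration in subjects who discontinued". If continued dosing does lengthen episodes, Group 2 would have more of them open at any cut-off. Averaging only resolved episodes would then remove more long values from Group 2 and pull the difference toward zero. In addition, a Group 1 episode whose dosing was suspended and which is still open at extension entry passes to Group 2 management, so its later duration no longer reflects Group 1. For ARIA-H, time to resolution fits poorly, because follow-up ends at stability.

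**Working it through.** The plan gives no figure for time to resolution, so there is none to reproduce. The check asks how much could be lost, first under a hard cut-off and then under the follow-up the protocol describes.

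**Inputs**

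- Onset (Protocol 4.3.2.1.3): "76% of subjects (35/46) developing the first episode within the first 6 months of active dosing", and 42/46 within 12 months. Of first-year episodes, 35/42 = 83% start within six months.
- Duration (same section): most ARIA-E resolved 4 to 12 weeks after onset. No mean, SD or distribution is given. The medians of 8 weeks (Group 1) and 12 or 16 weeks (Group 2) are assumptions.
- Episodes (16.7): a target of 25 subjects per group with moderate to severe asymptomatic ARIA-E.
- Dropout of 20% a year: an assumption; neither document gives a rate.

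**Step 1: observation stops at a fixed week.** Simulation of 400,000 episodes per setting; gamma, exponential, Weibull and two lognormal shapes; detection at Weeks 16/24/32/44/54 in 53/30/7/6/4%; durations rounded up to the 4-weekly MRI.

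| Shape, medians | True mean difference (weeks) | Resolved only, Week 54 |
|---|---|---|
| Gamma, 8 vs 12 | 5.0 | 2.7 |
| Gamma, 8 vs 16 | 10.2 | 4.5 |
| Weibull, 8 vs 12 | 4.3 | 4.0 |
| Exponential, 8 vs 16 | 11.6 | 3.1 |

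Over all settings the loss is 7% to 73% with a Week 54 cut and 3% to 55% with a Week 70 cut. A separate calculation, with assumed *means* of 8 against 12 or 16 weeks and a different onset spread, gave 2% to 49% over the two cuts.

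The length of observation drives these figures. For exponential durations with mean μ and a common window C after onset,

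E[T | T ≤ C] = μ − C·exp(−C/μ) / (1 − exp(−C/μ)).

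- C = 26: 6.95 (μ = 8) and 8.64 (μ = 12). The difference is 1.68 (unrounded values) against a true 4, a loss of 1 − 1.68/4 = 58%.
- C = 52: 7.92 and 11.31. The difference is 3.39, a loss of 1 − 3.39/4 = 15%.

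**Step 2: follow-up as the protocol describes it.** If every episode is followed to resolution, none is left out and the loss is 0%. With the assumed dropout, the weekly hazard is d = −ln(0.8)/52 = 0.00429. For exponential durations, episodes that resolve before dropout have mean 1/(1/μ + d), and the share left open is d/(1/μ + d).

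| μ (weeks) | Resolved-only mean | Share open | Open of 25 |
|---|---|---|---|
| 8 | 7.73 | 3.3% | 0.8 |
| 12 | 11.41 | 4.9% | 1.2 |
| 16 | 14.97 | 6.4% | 1.6 |

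The differences are 11.41 − 7.73 = 3.68 against 4 (8% lost) and 14.97 − 7.73 = 7.24 against 8 (about 10% lost). The simulation over all five shapes gives 2% to 13%.

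**Step 3: hand-over to the extension.** This affects only asymptomatic Group 1 episodes of the grades managed differently (moderate; severe as well in Stage 2) that are open at extension entry. With 25 such episodes and gamma durations, about 2.4 in Group 1 are open at Week 54. Hand-over or the assumed dropout takes about 3% to 14% of the mean difference.

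**Step 4: the median.** Both sets of descriptives quoted from the documents include the median. On the 4-weekly MRI grid, the resolved-only median changed in 1 of 30 settings.

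**Step 5: the direction.** Shrinkage requires that Group 2 episodes truly last longer and that follow-up and distribution shape are similar in the two groups. With exponential means of 8 and 12 weeks but windows of 18 and 52 weeks, the resolved-only difference is 5.4 instead of 4. With equal means of 10 weeks and windows of 12 and 26 weeks, a false difference of 3.1 appears.

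**Step 6: what would change.** SAP 2.5.2.3 and the list of planned tables contain no summary of time to resolution. A censoring rule would have no output to act on.

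**The case for a change.** The best case for a change is that the inconsistency sits within one paragraph. The authors chose a censored-data method for onset and not for resolution, on a named secondary endpoint where the background expects the groups to differ. Open episodes are foreseeable: an MRI is scheduled at Week 54, and ARIA first seen there cannot yet have resolved. Without a rule the direction of any bias is uncontrolled, as Step 5 shows. The remedy is a sentence or two, with the same data and standard software.

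Much of this stands. The gap is real, and the ARIA-H endpoint should have been worded as time to stabilization. Had the trial run its course, a full SAP would have needed to say that ARIA-E episodes are censored at withdrawal or at the last MRI before extension dosing, and to report how many stayed open.

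Three parts do not carry over. The large losses assume that observation stops at Week 54 or 70, against the follow-up rules. Nothing in the protocol says open episodes will be left out; that is inferred from a demographics paragraph and from a general SAP sentence qualified by the word generally. And no between-group difference in mean duration is planned, so the quantity said to be biased is not one the plan would report.

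**Conclusion.** No change is needed. The protocol leaves a detail unwritten that it expressly deferred to the SAP and that an analyst would fill in the usual way, by censoring open episodes and counting them. Under the documented follow-up to resolution, the possible understatement is nil with complete follow-up. It is about 2% to 14% of the mean difference when the assumed 20% annual dropout or the extension hand-over is allowed for. Those figures rest on assumed medians of 8 against 12 or 16 weeks, on Group 2 episodes truly lasting longer, and on similar follow-up in both groups; the documents support only a typical range of 4 to 12 weeks. The median is practically unaffected. The analysis itself was dropped after the study was terminated, so rewording Protocol 16.2.2.2 would change no table, listing or conclusion in the final report.
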